#### 5.2 Visit 2: Genicular Artery Embolization

The following data will be collected during each GAE procedure:

- Technical success of GAE, defined as successful catheterization and embolization
- Procedure time, duration of hospitalization, duration of catheterization, fluoroscopy dose, volume of embolic delivered, arteries embolized.

#### 5.3 Visits 3-7: Post GAE Follow-Up

Subjects will have the following assessments performed:

- Physical examination including vital signs
- WOMAC and VAS questionnaires (at visits 4-7)
- Review of adverse events
- Knee MRI (at visit 5: 3 month follow-up). If patients cannot undergo MRI (e.g. pacemaker, significant claustrophobia), then CT of the knee without contrast will be performed.
- Knee x-ray (at visit 7: 12 month follow-up)

# 6. Withdrawal of Subjects

Subjects will be informed that they have the right to withdraw from the study at any time for any reason, without prejudice to their medical care. The Investigator also has the right to withdraw patients from the study for any of the following reasons:

- Adverse Event
- Concurrent medical condition
- Patient unwillingness to comply with study requirements
- Patient death
- Other Investigator decision

If a patient is withdrawn or discontinued from the study, the reason for withdrawal will be recorded in the source documents and on the End of Study case report form (CRF). All patients withdrawn from the study will be encouraged to complete, if possible, all clinical evaluations scheduled for the 12-month follow-up visit. All adverse events will be followed as described in Section 7. Patients who are withdrawn from the study for any reason will not be replaced. The Principle Investigator may terminate the study at any time.

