# 2. Study Objectives

# 2.1 Primary Objective

The primary objective of this investigation is to assess safety of genicular artery embolization (GAE) for knee osteoarthritis (OA) using Embozene particles.

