# 4. Study Design

This is a single-center, prospective, single arm investigational study to evaluate the safety of genicular artery embolization (GAE) for treatment of symptomatic knee osteoarthritis (OA). In addition, the improvement as part of efficacy will be reported. All subjects will have either failed or be intolerant to conservative management, and be ineligible for or refuse surgical intervention. Subjects will be considered enrolled in the study once they have provided informed consent and have been determined to meet all eligibility criteria. A total of 40 subjects will be enrolled in the single treatment arm of the study and will be followed for 12 months. The subjects will be stratified according to arthritis severity based on imaging, with 20 subjects allocated to mild-moderate arthritis based on x-ray (Kellgren-Lawrence x-ray grade 1-2), and with 20 subjects allocated to severe arthritis based on x-ray (Kellgren-Lawrence x-ray grade 3-4). The stratification will not be randomized, but each category will be limited to 20 patients.

The study will involve a screening period in which patient eligibility is determined. Once eligibility is confirmed, subjects will undergo GAE with Embozene microspheres (100 micron). Following treatment, subjects will return for follow-up visits at 1 week (± 4 days), 1 month (± 2 weeks), 3 months (± 2 weeks), 6 months (± 2 weeks), and 12 months (± 2 weeks) post-procedure. At these visits, subjects will complete the Western Ontario and McMaster Universities Osteoarthritis Index (WOMAC) score, and a visual analog scale (VAS) score, undergo a directed physical examination, and report any new adverse events (AEs). At 3 months of follow-up, subjects will also undergo knee x-ray. At the 12 month follow-up, subjects will also complete a patient-reported outcomes (PRO) and patient global impression of change (PGIC) questionnaire.

The primary objective of the study will be to assess safety via minor and major adverse events. Secondary objective will be improvement of OA symptoms as assessed by the WOMAC and VAS scores at each follow-up visit. Subjects will continue to be followed according to the institutional standard of care after they complete the 12-month study visit.

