Every effort will be made to minimize risks of the procedure. Since the embolization is being performed in a branch off of the femoral or popliteal artery in the knee, many of the risks listed on the IFU do not apply to the intended use in the protocol. For example, "migration of the microspheres to other parts of the body" cannot occur since the procedure is being done in an extremity, unlike a liver embolization for liver tumors where collateral vessels are present. The use is for arterial embolization, and deep vein thrombosis or pulmonary embolism only occurs in the setting of Embozene embolization of a vascular malformation, where there is an inherent abnormal communication between arteries and veins. Ischemic stroke or neurological deficit should only occur if embolization is being performed in the head or neck, and since the embolization is being performed in the knee, this risk does not apply. The risks of radiation from this procedure is exceedingly low, since angiography is only being performed on the extremity. Therefore, vital solid (eyes, thyroid) and reproductive organs (ovaries, testicles) are not in the field of view. Angiography of the extremity tends to involve extremely low amounts of radiation due to the lack of fat and muscle (compared to the abdomen) needed to penetrate for the x-rays. Finally, death from the use of this device has only been reported in embolization of high-risk regions, such as the lungs or brain. Since the procedure is being performed in the knee, there is no risk of death in this study.

An MRI (or CT) of the knee will be performed during follow up, for the purposes of detecting any sequela of non-target embolization, or other unexpected abnormality. It is likely that there will be no changes in the MRI or CT appearance compared to baseline.

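### Section 6 does not separate leaving the study from ending safety follow-up, so interim adverse-event reviews and the month-3 MRI/CT can be missed in treated patients who had harm

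*Combined protocol and SAP*

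**What the plan says.** The primary objective (Section 2.1) is "to assess safety of genicular artery embolization (GAE) for knee osteoarthritis (OA) using Embozene particles". Treatment is a single procedure. Section 4 states "Once eligibility is confirmed, subjects will undergo GAE with Embozene microspheres (100 micron"), and Appendix A marks the embolization at Visit 2 only.

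On withdrawal, Section 6 states: "The Investigator also has the right to withdraw patients from the study for any of the following reasons". The first entry in the list is "Adverse Event". A concurrent medical condition and a general investigator-decision entry are also there. The section does not distinguish patients awaiting the procedure from patients who have had it.

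Two things are kept after withdrawal. Patients "will be encouraged to complete, if possible, all clinical evaluations scheduled for the 12-month follow-up visit", and adverse events are followed as Section 7 describes. Section 7.2 follows events judged related to the procedure or device until they resolve or the patient dies.

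The only follow-up MRI is set in Section 5.3: "Knee MRI (at visit 5: 3 month follow-up"), with CT as the substitute. Section 7.4 gives its purpose: "An MRI (or CT) of the knee will be performed during follow up, for the purposes of detecting any sequela of non-target embolization". The imaging at month 12 is an x-ray (Section 5.3, Appendix A).

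Withdrawn patients are not replaced (Section 6). Section 9 assumes no loss to follow-up and has no rule for how withdrawn patients enter the adverse-event rates.

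**The concern.** When treatment is repeated, an adverse event may be a reason to stop giving it. Here the treatment is complete on Day 1. Withdrawing a treated patient from the study because of an adverse event changes nothing about exposure and removes only observation. The rule therefore permits follow-up to end because of the outcome that the study is meant to measure.

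At stake are the harms that appear after the event that led to withdrawal: a second adverse event, or a sequela visible only on the month-3 scan. The event behind the withdrawal is already recorded and counts under its own type and severity. If the all-event composite is counted per patient, that patient is already in it. The exposure is in the rates by type and severity, the individual event rates and the MRI findings. With 40 patients and no replacement, one or two missed findings would be visible in the results.

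**Working it through.** **No plan figure to reproduce.** The documents give no withdrawal rate, no expected sequela rate and no bias calculation. The power and precision figures in Section 9 assume complete follow-up, and this point does not depend on them.

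**What is kept after a withdrawal that follows the procedure** (Sections 5.3, 6, 7.1, 7.2 and Appendix A):

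- *Known, related adverse events:* kept, to resolution or death.
- *Adverse-event review at week 1, month 1, month 3 and month 6:* no provision. Section 7.1 relies on patients reporting events at each visit, and Section 6 keeps none of these visits.
- *Month-3 MRI/CT:* no provision if withdrawal comes before month 3. If withdrawal comes after the scan, nothing is lost here.
- *Month-12 visit (examination, adverse-event review, questionnaires, x-ray):* encouraged, if possible. Section 6 does not say whether these evaluations are done at withdrawal or at month 12. If at withdrawal, questioning about new events ends that day.

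On the timing of imaging, Section 4 mentions a knee x-ray at 3 months, while Section 5.3 and Appendix A agree on MRI at month 3 and x-ray at month 12. The reading above follows the latter two. The sections should be reconciled.

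**Direction of the possible error.** Let n patients be treated and s have a sequela that the scan would show. Let k be withdrawn before month 3 without a scan, m of them with a sequela.

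- Over all treated, the reported rate is (s − m)/n. This is never above s/n.
- Over scanned patients only, it is (s − m)/(n − k). This is below s/n exactly when m/k > s/n, and above it when m/k < s/n.

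**Illustration with assumed counts.** Take n = 40 (Section 4) and assume s = 4 and k = 2. The true rate is 4/40 = 10.0%.

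| Withdrawn patients with a sequela (m) | Over all treated | Over scanned only |
|---|---|---|
| 2 | 2/40 = 5.0% | 2/38 = 5.3% |
| 1 | 3/40 = 7.5% | 3/38 = 7.9% |
| 0 | 4/40 = 10.0% | 4/38 = 10.5% |

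The result thus runs from half the true rate to slightly above it, according to an assumption that the documents do not inform.

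**Loss of precision against selective loss.** With no findings among N scanned patients, the exact two-sided 95% upper bound is 1 − 0.025^(1/N). This gives 8.8% at N = 40, 9.3% at N = 38 and 9.7% at N = 36. Losing a few scans at random costs little. Selective loss costs more. If the 2 withdrawn patients were the only ones with a sequela, the study would show 0/38 with an upper bound of 9.3%. Complete follow-up would show 2/40 = 5.0% (exact 95% CI 0.6% to 16.9%).

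**The case against.** The strongest reply is that the rule is a right and not a trigger. No adverse event requires withdrawal, and the investigators may never use the rule this way. Related events are still followed, and the encouraged 12-month visit includes an adverse-event review and an examination, so a patient who attends at month 12 is asked about new events. A patient withdrawn after month 3 has already been scanned. All of this stands, and it limits the point to what can be missed.

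A reader might infer that patients with harm will lose their safety follow-up. The documents do not support that: withdrawal is discretionary and part of the follow-up is kept.

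A reader might also infer that the error always runs towards fewer harms. That is true of counts over all treated patients. It fails for rates among scanned patients, as 4/38 = 10.5% against 10.0% shows. Section 7.1 defines adverse events regardless of cause, so patients withdrawn for one need not carry a higher risk of sequelae. No passage says that they do, and Section 7.4 expects the follow-up scan to look like baseline in most cases.

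Finally, deleting the adverse-event and concurrent-condition entries may look like the obvious remedy. It is not. Patients count as enrolled once they have consented and are eligible (Section 4), and screening may precede the procedure by up to 8 weeks (Section 5.1). For an enrolled, untreated patient these are ordinary reasons to withdraw. Deletion would also leave the general investigator-decision entry, which allows the same withdrawals after the procedure.

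**Conclusion.** The gap is real and textual. After the procedure, Section 6 treats withdrawal from the study as the end of scheduled safety follow-up, apart from related-event follow-up and an encouraged 12-month visit without MRI/CT. Interim adverse-event reviews, and the month-3 scan when withdrawal comes earlier, can be missed in patients who had harm. Counts of further adverse events and MRI sequelae over all treated patients could then be too low. Rates among scanned patients only could move either way.

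The size cannot be estimated from the documents. It is zero if no treated patient is withdrawn early or if those withdrawn have no further harm. The 5.0% against 10.0% illustration rests wholly on assumed counts. Since safety is the primary objective, only 40 patients are treated and the remedy is wording, this is a cheap improvement worth making.

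**What to change.** Keep the list of reasons in Section 6 for patients not yet treated. Then add, for patients who have had the embolization:

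- An adverse event, a concurrent condition or another investigator decision does not end safety follow-up. Adverse-event review at each remaining scheduled visit (by phone if needed) and the month-3 MRI/CT continue to month 12 unless the patient withdraws consent or dies.
- For patients who still leave before month 3, the MRI/CT joins the evaluations they are encouraged to complete.

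A sentence in Section 9 on how withdrawn patients count in the numerators and denominators of the adverse-event and MRI rates would also help, because the direction of any error depends on it.

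The cost is a wording amendment and some effort to retain patients who would otherwise be closed out. No visit or scan is added beyond those already scheduled. Section 5 already allows phone follow-up at months 3, 6 and 12 under pandemic travel restrictions, so adverse-event review by phone extends an existing provision.

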# 7. Adverse Events

# 7.1 Definitions

Adverse Event: An adverse event (AE) is any untoward medical occurrence in a patient regardless of any causal relationship with a study treatment or procedure. An AE can therefore be any unfavorable or unintended sign, symptom, or disease temporally associated with the use of a medicine or a procedure, whether or not considered related to the product or procedure. A non-serious AE is any untoward medical occurrence that does not meet any of the criteria for a serious adverse event as defined below.

Laboratory data will be collected as described in this protocol. Clinical syndromes associated with laboratory abnormalities are to be recorded as appropriate.

Patients will be instructed to report AE that they experience to the Investigator or Study Coordinator at each visit. AEs occurring during the trial and the protocol-defined 12-month follow-up period will be reported on the AE case report form (CRF). The Investigator will record AE terms according to Medical Dictionary for Regulatory Activities (MedDRA) lowest level terms. Whenever possible, a specific disease or syndrome will be reported rather than the associated signs and symptoms. Independent signs and symptoms will be reported as separate AEs.

All AEs will be assessed for severity, relationship to the study treatment, treatment required and outcome/resolution. This information will be reported on the AE CRF.

Serious Adverse Event: A serious adverse event (SAE) is any AE, occurring at any dose and regardless of causality, that:

- Results in death
- Is life-threatening, such that the patient was at immediate risk of death from the event as it occurred
- Requires inpatient hospitalization or prolongation of existing hospitalization; note that hospital admissions and/or surgical operations scheduled to occur during the study period but planned prior to study entry are not considered AEs if the illness or disease was diagnosed before the patient was enrolled in the study (provided that the patient's condition does not deteriorate in an unexpected manner during the study)
- Results in persistent or significant disability or incapacity, such that the patient experiences a substantial disruption of their ability to perform normal functions
- Is an important medical event as determined by the Investigator. An important medical event is an event that may not result in death, be life-threatening or require hospitalization, but may be considered an SAE when, based upon appropriate medical judgment, it may jeopardize the patient and may require medical or surgical intervention to prevent one of the outcomes listed above.

Under this protocol, scheduled hospitalizations or elective surgical procedures will not be considered SAEs. Complications associated with surgical procedures or study treatments resulting in one of the outcomes above are considered SAEs.

#### 7.2 Adverse Event Reporting

The Investigators are responsible for monitoring the safety of patients who have been enrolled in the study. All AEs considered to be related to the procedure or study device will be followed until the event resolves or has reached a fatal outcome. AEs will be evaluated for severity using the standardized terms "mild," "moderate" and "severe."

The Investigators will document all AEs occurring during the study, commencing with the date of the GAE treatment and including the protocol-defined 12-month follow-up period. AEs and SAEs that occur following the signature of informed consent but prior to treatment will not be captured or reported.

#### 7.3 Serious Adverse Event Reporting

Any unanticipated SAE, including death due to any cause that occurs during the study treatment or initial 12-month follow-up period, related to the procedure or study device, will be reported to the FDA within 3 days of the site learning of the event.

Unrelated SAEs will be reported at the FDA IDE annual report. The SAE must be completely described on the AE CRF as well as the Serious Adverse Event Form.

All safety concerns should be reported to:

[name] [name] [contact] [contact]

7.4 Potential adverse events

#### Commonly observed

Blood draw:

- Temporary pain from the needle stick
- Bruising or swelling at the site

#### MRI:

• Feeling of claustrophobia

#### Angiogram:

• Temporary pain at the insertion site

Genicular artery embolization:

- Temporary discoloration of the skin (less than 2 weeks)
- Temporary soreness in the knee (less than 2 weeks)

#### Less likely

Blood draw:

• Fainting

Angiogram:

- Allergic reaction to contrast dye
- Reaction to sedative medications (for example: nausea, itching)

## Rare but serious

Blood draw:

• Infection

# MRI:

• Potential heating or movement of any metal in the body

## Angiogram:

- Possible risk of a blood clot in the artery
- Bleeding around the catheter insertion site
- Damage to the artery itself.
- Risk of ionizing radiation (typically less than a CT scan)

## Genicular artery embolization:

- Infection
- Prolonged severe pain
- Injury to the knee (osteonecrosis)
- Allergic reaction to Embozene Microspheres
- Sequela of non-target embolization (skin necrosis, toe necrosis).

# Warnings/complications on the Embozene Microsphere IFU include:

- Undesirable reflux or passage of Embozene into normal arteries adjacent to the target or through the lesion into other arteries or arterial beds.
- Embolization of the wrong artery or migration of the microspheres to other parts of the body, which may necessitate further treatment.
- Hematoma, or bruising, at the incision site for arterial access.
- Arterial aneurysm or thrombosis at the incision site for arterial access.
- Deep vein thrombosis, or clotting of a deep vein in patient's leg.
- Pulmonary embolization
- Ischemia at an undesirable location
- Capillary bed saturation and tissue damage.
- Ischemic stroke or ischemic infarction
- Vessel or lesion rupture and hemorrhage
- Neurological deficit including cranial nerve palsies.
- Vasospasm
- Recanalization
- Foreign body reactions necessitating medical intervention
- Infection necessitating medical intervention
- Clot formation at the tip of the catheter and subsequent dislodgement
- Allergic reaction
- Risks of radiation from angiography and fluoroscopy used to visualize the blood vessels during embolization, which may include a radiation burn and risks to future fertility.
- Death

Many of these risks may not apply, since these risks are from embolizing areas in the lungs or brain.

Every effort will be made to minimize risks of the procedure. Since the embolization is being performed in a branch off of the femoral or popliteal artery in the knee, many of the risks listed on the IFU do not apply to the intended use in the protocol. For example, "migration of the microspheres to other parts of the body" cannot occur since the procedure is being done in an extremity, unlike a liver embolization for liver tumors where collateral vessels are present. The use is for arterial embolization, and deep vein thrombosis or pulmonary embolism only occurs in the setting of Embozene embolization of a vascular malformation, where there is an inherent abnormal communication between arteries and veins. Ischemic stroke or neurological deficit should only occur if embolization is being performed in the head or neck, and since the embolization is being performed in the knee, this risk does not apply. The risks of radiation from this procedure is exceedingly low, since angiography is only being performed on the extremity. Therefore, vital solid (eyes, thyroid) and reproductive organs (ovaries, testicles) are not in the field of view. Angiography of the extremity tends to involve extremely low amounts of radiation due to the lack of fat and muscle (compared to the abdomen) needed to penetrate for the x-rays. Finally, death from the use of this device has only been reported in embolization of high-risk regions, such as the lungs or brain. Since the procedure is being performed in the knee, there is no risk of death in this study.

An MRI (or CT) of the knee will be performed during follow up, for the purposes of detecting any sequela of non-target embolization, or other unexpected abnormality. It is likely that there will be no changes in the MRI or CT appearance compared to baseline.

# 8. Symptom Assessment

8.1 Western Ontario and McMaster Universities Osteoarthritis Index (WOMAC, version 3.1)

The Western Ontario and McMaster Universities Osteoarthritis Index (WOMAC) is a widely used, set of standardized questionnaires used by health professionals to evaluate the condition of patients with osteoarthritis of the knee and hip, including pain, stiffness, and physical functioning of the joints. It can be self-administered and was developed at Western Ontario and McMaster Universities in 1982.

The WOMAC measures five items for pain (score range 0–20), two for stiffness (score range 0–8), and 17 for functional limitation (score range 0–68). Physical functioning questions cover everyday activities such as stair use, standing up from a sitting or lying position, standing, bending, walking, getting in and out of a car, shopping, putting on or taking off socks, lying in bed, getting in or out of a bath, sitting, and heavy and light household duties.

A WOMAC test takes about 12 minutes, and is among the most widely used assessments in arthritis research.

A copy of the WOMAC (version 3.1) is provided in Appendix D.

